4.7 Early Termination

If the participant, legal guardian, or the study physician make the decision to have the participant exit the study early, a follow-up visit must be scheduled 28 days (+/- 14 days) after termination. At this visit, the study physician should review the patient's medical history, concomitant medications, and the DOTES. If the patient exited the trial due to an adverse event, this event should be reviewed and if it is still present the study team must follow-up with the patient/legal guardian for 56 days or until the event has subsided. At the completion of this follow-up visit, the participant may be unblinded and the results may be disclosed to the participant.

5. Recruitment Methods

Recruitment will leverage the observational study, The Natural History of Individuals with Autism and Germline Heterozygous PTEN mutations, and will occur at 3 sites: Cleveland Clinic, Stanford University, and Boston Children's Hospital, with Cleveland Clinic expected to recruit at least 50% of the sample based on extensive experience with PTEN patients at this site. Over the last 5 years, we have recruited and comprehensively evaluated 35+ patients with PTEN ASD only from referrals to Cleveland Clinic and word of mouth. We anticipate that the majority of these individuals would participate in the proposed study.

We will supplement our current recruitment efforts with several complementary strategies. First, [name] (Cleveland Clinic) has developed a registry of > 400 individuals with PTEN mutations that includes > 50 PTEN cases with ASD or evidence of developmental delay. To date, this registry has not been tapped, but it will be used to recruit individuals for the proposed study. [name] lab also regularly screens individuals at risk of PTEN mutations using an online risk calculator and extensive referral network – growing her registry. Second, the two additional sites, Stanford University and Boston Children's Hospital, also have experience with PTEN ASD patients and have an identified population that is interested in participating in this trial. Both of these sites will also leverage their relevant clinics to advertise and recruit for this study. Third, we have obtained support

from a community for caregivers of PTEN ASD patients (www.ptenlife.com) and the largest online group devoted to supporting families and patients affected with and by PHTS (www.ptenworld.com). Both groups have agreed to assist in recruitment. Finally, we will employ multiple advertising and recruiting tools both locally and nationally to raise awareness of the study.

Potential subjects will be recruited through the same methods as listed above at the other participating sites. Recruitment will begin as soon as IRB approval is obtained.

The study coordinator, principal investigator, co-investigators and sub-investigators at each site will be responsible for recruitment efforts. An introductory letter to families with known diagnosis of PTEN and who otherwise meet eligibility criteria with an opt-out postcard as well as advertisements on advocacy group websites will be utilized for recruitment at each site. We will also utilize the Rare Diseases Clinical Research Network Developmental Synaptopathies Consortium (RDCRN DSC) contact registry, developed as a part of the natural history study, to inform individuals interested in research opportunities about the trial. This registry already has more than 80 distinct patients entered.

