2.1 Primary objective

To evaluate the safety of everolimus compared with placebo in patients with PTEN mutations focusing on NCI CTCAE Grade 3 and 4 adverse events, serious adverse events, and Grade 3 and 4 laboratory toxicities. The primary endpoint will be study drop-out rate due to side effects, comparing everolimus vs. placebo. Based on the published literature and our experience in prior TSC trials we hypothesize that the drop-out rate due to side effects in those receiving everolimus will be similar to those in the placebo group with minimal effect size (< 10% difference). We will also determine the frequency of adverse events by type and severity. We predict that the rate of adverse events will be no more than 10% higher in the everolimus group compared to placebo, but overall severity will be minimal.

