Tests that will be conducted during the blinded treatment phase include laboratory tests for safety, physical exams (including a neurological assessment), vital signs, and neuropsychological assessments. If unforeseen circumstances (i.e., unexpected personal reasons) prevent the patient from complying with the established visit schedule, the site can re-schedule the visit (within \pm 14 days of the expected visit date). The reason(s) for any visit or treatment delays will be documented in the CRF for the appropriate visit. All on-site visits (screening,

baseline, month 1, month 3, and month 6) must be completed by the participant, and any missed visits would warrant termination from the study. A summary of the neuropsychological results may be made available at study completion.

At the end of the double-blind phase (or early termination), the treatment code will be broken and the participant will be informed of their assigned treatment arm, using the process outlined in the 7904 Manual of Procedures. Participants who received the active compound will enter the follow-up phase of the study (section 4.5) and will be referred back to their treating physicians. Individuals who were in the placebo group will be invited to enter Phase B, a 6-month open-label extension trial (section 4.4). The inclusion of the open-label phase may increase the acceptability of the project by families and increase their participation in the primary, controlled trial. All participants that received everolimus during the blinded treatment phase will enter the follow-up phase of the trial and will be referred back to their treating physicians. A summary of patient's participation in the study will be provided, if needed.

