7.6 Double-Blind Treatment Assignment Unblinding

Prior to the Month 6 visit or early termination, the site will obtain the unblinded treatment assignment via the procedures described in the 7904 Manual of Procedures. At the conclusion of the double-blind phase or early termination, the blind will be broken immediately. Individuals on the active drug will exit the study, and those who were on placebo will be invited to join the open label phase (section 4.4).

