7.7.6 Study Drug Interruption or Discontinuation

An intent to treat approach will be used. All data acquired prior to termination for the reasons outlined below will be included in the primary analysis unless patient withdraws consent. Every effort will be made to conduct a final study visit with the participant and participants will be followed clinically until, if applicable, all adverse events resolve.

The term "interruption" refers to a patient stopping the study medication during the course of the study, but then re-starting it at a later time in the study (as determined by their study doctor).

The term "discontinuation" refers to a patient's premature and permanent withdrawal from the study treatment. The reason for discontinuation from treatment will be recorded. The patient may discontinue participation in the study for any of the following reasons:

- 1. adverse event(s)
- 2. abnormal laboratory value(s)
- 3. abnormal test procedure result(s)
- 4. protocol deviation
- 5. subject withdrew consent
- 6. Withdrawal by the investigator
- 7. lost to follow-up
- 8. administrative problems
- 9. intercurrent illness or event that precludes further visits to the study site or ability to evaluate disease (e.g.-mental status change, large pleural effusion).
- 10. death

If a patient has discontinued the study drug due to an unacceptable adverse event or an abnormal laboratory value, he/she should not have withdrawal of consent recorded as the reason for discontinuation. Instead, the reason for discontinuation must be recorded as due to adverse event or abnormal laboratory value.

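### Sections 4.3, 7.5 and 7.6 unblind early terminators at exit while 4.7 waits for a follow-up visit, so the coded reason behind the primary endpoint can be entered with the arm known

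*Combined protocol and SAP*

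**What the plan says.** Four sections bear on when a patient who leaves the double-blind phase early is unblinded.

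- Section 4.7: "a follow-up visit must be scheduled 28 days (+/- 14 days) after termination". The physician then reviews medical history, concomitant medication, the DOTES and any adverse event that led to the exit. The section ends: "At the completion of this follow-up visit, the participant may be unblinded and the results may be disclosed to the participant".
- Section 4.3: "At the end of the double-blind phase (or early termination), the treatment code will be broken and the participant will be informed".
- Section 7.6: "Prior to the Month 6 visit or early termination, the site will obtain the unblinded treatment assignment". It continues: "At the conclusion of the double-blind phase or early termination, the blind will be broken immediately".
- Section 7.5 keeps the allocation confidential until unblinding at discontinuation or until the final analysis.

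Two other places, the placebo dose-adjustment text in section 6 and section 7.16.8, say that the site team stays blinded throughout.

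The endpoint concerned is in section 2.1: "The primary endpoint will be study drop-out rate due to side effects, comparing everolimus vs. placebo". Section 7.7.6 requires a reason for each discontinuation and lists ten. For a patient who stops because of an unacceptable adverse event or laboratory value, it says that "the reason for discontinuation must be recorded as due to adverse event or abnormal laboratory value", and not as withdrawn consent. Section 13.1 asks for a yes/no judgement of relatedness for each adverse event.

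**The concern.** Whether an exit was due to side effects is a judgement, and that judgement is the primary endpoint. A patient may leave with a mild adverse event, a family reason and doubts about benefit all at once. Someone who knows the patient was on everolimus may be readier to name the adverse event as the cause, and someone who knows it was placebo less ready. Relatedness and the DOTES review after exit are open to the same influence.

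The sections cannot all be followed. Three sites could therefore handle the same kind of patient differently, some coding blind and some not. With few exits expected, the endpoint has little capacity to absorb such differences.

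**Working it through.** **Step 1. The order of events under each set of sections.**

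| Event | Under 4.7 | Under 4.3, 7.5 and 7.6 |
|---|---|---|
| Site obtains the code | After the follow-up visit | Before or at termination |
| Reason for leaving recorded | Before any code break | Order not stated; may follow the code |
| Relatedness of events behind the exit | Before any code break | Order not stated; may follow the code |
| Follow-up review, including DOTES | Arm unknown | Arm known |
| 56-day follow-up of a persisting event | Arm may be known | Arm known |

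The follow-up visit falls between day 28 − 14 = 14 and day 28 + 14 = 42 after termination. Under 4.3 and 7.6 that whole interval is unblinded.

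**Step 2. Does any other section set the order?** Section 7.7.6 requires the reason to be recorded but does not place this before the code break. Section 13.1 is silent in the same way on relatedness. Section 13.4 gives final causality of serious events to the medical monitor, but the drop-out reason and non-serious relatedness have no such central step.

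**Step 3. Do early terminators need the code at once?** Section 4.6.3 admits to open label only placebo patients who completed the double-blind phase, so early terminators do not qualify. Emergencies are covered by 7.6.1. The immediate break serves no evident purpose for this group.

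**Step 4. Scale.** The plan's own safety power is a check on the basis used. For 1/20 v 8/20, one-sided α = 0.05, section 17.1 states 0.81; exact power of the one-sided Fisher test with 20 per arm is 0.808. It reproduces, and no figure in the plan is disputed here.

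Inputs: 20 per arm; overall drop-out about 10% (17.1); a difference of 10% or more is treated as meaningful and reported (17.1).

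- Expected exits: 0.10 × 40 = 4.
- One exit in one arm: 1/20 = 5 points.
- Two differently coded exits: 2 × 5 = 10 points. For example, suppose two patients leave in each arm and blind coding would give 1/20 v 1/20. Moving one everolimus exit into the side-effect category and one placebo exit out of it gives 2/20 v 0/20, a difference of 10 points.

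One-sided Fisher p-values with 20 per arm:

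- 2 v 0: C(20,2)/C(40,2) = 190/780 = 0.244
- 2 v 2: 0.70
- 4 v 0: C(20,4)/C(40,4) = 4845/91390 = 0.053
- 5 v 1: 0.091
- 6 v 1: 0.046

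A single recoded exit can cross 0.05 (5 v 1 to 6 v 1). That needs seven side-effect exits, against about four exits of any kind expected.

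**The case against.** Several points on the other side are sound.

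- A reader might infer that the reason for leaving stays open until the 28-day visit and is settled there with the arm known. The documents do not support that. Section 7.7.6 ties the reason to the discontinuation, and 4.7 is written as if the reason is already known at the visit. The exposure of the reason comes from 7.6, which gives the site the code before termination.
- A reader might also infer that arm-aware coding would decide the primary result. The splits of 2 v 0 and 4 v 0 are constructed extremes and neither falls below 0.05; four exits per arm would be 8/40 = 20%, twice the assumed rate. Section 17 calls the analyses predominantly descriptive, and the 10-point figure triggers reporting and is not a pass/fail rule.
- Section 17 also compares drop-out for any reason, with its own Kaplan-Meier analysis. Coding of the reason cannot change that comparison, so in the example above the equal 2 v 2 would be visible.
- Section 7.7.6 closes one route of discretionary coding, by barring withdrawn consent for an adverse-event exit. It still leaves someone to judge whether the event caused the exit.
- Section 4.7 says the patient *may* be unblinded after the visit. Delay is the natural reading, not an explicit ban on earlier release.
- Sections 4.3 and 7.6 refer to the Manual of Procedures, which is not among the documents and may set the order. The protocol sections would still contradict each other.

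These points limit the size of the concern. They do not remove the contradiction or supply the missing order of events.

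**Conclusion.** The point holds as an inconsistency that leaves the primary endpoint unprotected. For early terminators, three sections place unblinding at exit, one places it 14 to 42 days later, and two statements elsewhere have the site blinded throughout. No section requires the reason or relatedness to be entered before the code is obtained.

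The possible effect is bounded only by the number of exits, at 5 points each in an arm of 20. Two differently coded exits are enough for the 10-point reporting threshold. This assumes 20 per arm and about 10% drop-out, as in section 17.1. It is a measure of sensitivity, not a forecast: the documents allow the bias and do not show that it would happen. The correction is worth making because it is cheap and concerns the primary endpoint.

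**What to change.** Reconcile 4.3, 7.5 and 7.6 with 4.7 for patients who leave the double-blind phase early:

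1. At termination, the reason for drop-out and the relatedness of adverse events are entered and locked before the site can obtain the assignment.
2. The follow-up visit review, including the DOTES, is entered next. Only then is the code released. State this in 4.7 as a requirement in place of *may*.
3. For patients who do not attend, the code is released once the follow-up window has closed (day 42). A rule is needed because 7.7.6 foresees patients who refuse to return.
4. Emergency unblinding under 7.6.1 is unchanged.

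Amending only 4.3 and 7.6 would leave the conflicting wording in 7.5. The statements that the site is always blinded (section 6 and 7.16.8) should be read, or reworded, as holding until release.

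The cost is a few sentences in an amendment, a database lock step, and a wait of about two to six weeks before early leavers learn their arm. The change does not blind all follow-up. Completers, about 40 − 4 = 36 patients, would still know their arm at the 28-day call, and the 56-day follow-up of persisting events would still come after unblinding. It protects the coding of drop-out, which arises only for early terminators.

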5.1 Retention Strategies

To retain participants throughout the 6-month trial, sites will use procedures that have proven successful in previous studies, such as phone calls to debrief after the most recent visit and phone calls or emails to prepare for the upcoming visit. Individual sites will seek IRB approval for each of the methods that they use prior to distribution. Whenever possible, study staff at each site should also try to schedule study visits on a day that is convenient for the family. Additionally, caregivers, or adult participants, will receive feedback on their child's, or their, neurocognitive profile and changes over time at the end of the trial. Since there is a 50/50 chance of participants receiving everolimus or placebo, it is important for study staff to make sure the family is aware of the open-label phase of the study. Families should also be reminded that all travel expenses, throughout the entirety of the trial, will be covered. Finally, study staff should always express gratitude and thanks to both the patient and his/her family for participation in the study.

6. Description of Study Treatments or Exposures/Predictors

6.1 Everolimus Administration

Patients will be randomized to receive either everolimus or placebo. Patients will be treated with blinded study treatment for 6 months, or until unacceptable toxicity or discontinuation for any other reason.

For the duration of the trial, everolimus and placebo will be supplied to the research pharmacies at each site directly from Novartis. Everolimus and placebo will be formulated as identical tablets of 2.5mg or 5mg strength, blister-packed under aluminum foil in units of 10 tablets. Medication labels will comply with US legal requirements for investigational drug products and will be printed in English. The storage conditions for study drug will be described on the medication label.

The study drug everolimus and/or placebo will be self-administered (by the patient or patient's parent/guardian). The investigator should promote compliance by instructing the patient to take the study drug exactly as prescribed and by stating that compliance is necessary for the patient's safety and the validity of the study. The patient should be instructed to contact the investigator if he/she is unable, for any reason, to take the study drug as prescribed. Everolimus should be administered orally once daily at the same time every day, consistently with a light, low-fat meal. Everolimus or placebo tablets should be opened only at the time of administration as drug is both hygroscopic and light-sensitive. The extent of absorption of everolimus through topical exposure is not known. Therefore, patients/caregivers are advised to avoid contact with the everolimus or placebo tablets and should wash their hands thoroughly before and after administration.

For the Open-label phase: Everolimus is formulated as tablets for oral administration of 2.5mg, 5mg, and 10mg strength. Tablets are blister-packed under aluminum foil, which should be opened only at the time of administration as drug is both hygroscopic and light-sensitive. Refer to label for expiration date and storage conditions.

The average starting dose will be 4.5 mg/m²/day of trial therapy (either everolimus or placebo), rounded to the nearest 2.5mg dose. The BSA should be calculated (section 7.15) based on an accurate height and weight measurement performed according to institutional guidelines. Leftover study medication, as well as all used blister packs, should be collected at each study visit, and drug should be accounted for at this time. If 2.5mg tablets become unavailable during the trial, patients prescribed a dose including 2.5mg tablets will be instructed to alternate between a higher and lower dose. The site physician will instruct the patient to take the higher dose on Monday, Wednesday, and Friday. The patient will take the lower dose on Tuesday, Thursday, Saturday, and Sunday. For example, a patient prescribed a dose of 7.5mg will take 10mg on Monday, Wednesday, and Friday, and 5mg on Tuesday, Thursday, Saturday, and Sunday.

A maximum volume of 3 ml of blood will be drawn for trough everolimus PK levels when necessary. The blood draws will be timed to occur at 24 ± 4 hours after ingestion of the drug. Blood collection for PK samples may be conducted during a scheduled visit on-site or via a designated and trained remote healthcare service. Everolimus levels will be measured at ARUP laboratories in Salt Lake City, UT, in conjunction with LabConnect, LLC. When necessary, a kit for remote collection of blood samples can be sent to the participant and returned per the shipping instruction by express mail.

Dose adjustments in the blinded phase of the trial can occur in both placebo (randomized modification) and active (based on PK findings) arms and will be at the discretion of a central unblinded investigator, [name]. or back-up unblinded investigator, [name]. In the event both Drs. [name] and [name] are unavailable, [name], Medical Review Officer, will serve as the unblinded investigator for the purposes of PK-driven dose adjustments. An unblinded research nurse will assist the unblinded physicians and the Medical Review Officer in their roles and will make sure that communications between them and the different sites is occurring in a timely manner.

Dose adjustments will be permitted, based on safety findings and PK levels. The site PI will initiate any safety level related dose adjustments according to the protocol, in collaboration with the Medical Review Officer as appropriate. PK based dose adjustments will be initiated by the unblinded physician. All dose adjustments will be made using the 2.5mg tablets (i.e. increase by 2.5mg, decrease by 2.5mg, or maintain dose). If a dose adjustment is made for safety purposes, the unblinded physicians and Medical Review Officer should be made aware of any dose modifications as soon as possible.

Sites may substitute 5mg tablets (or 10mg tablets in open label) for 2.5mg tablets where necessary, as long as the single dose level increase or decrease is maintained. For example, an adjustment from 7.5mg to 10mg can be made by prescribing two 5mg tablets (or one 10mg tablet in open label) rather than one 5mg and two 2.5mg tablets. Following a dose adjustment, sites can mail the extra 5mg tablets to the participant in between visits to make up for the remaining days until the next site visit. One level dose increase would be increasing the dose by 2.5mg and a one level dose decrease would be decreasing the dose by 2.5mg as stated above.

Placebo Arm: Placebo dose adjustment procedures are defined in the unblinded dose adjustment protocol – accessible only to the unblinded physician(s) and the DMCC. The site team will be blinded with respect to treatment assignment at all times. [name], [name], and [name] will receive instructions regarding dose modifications for participants on placebo from the DMCC. When PK values become available for individuals in placebo arm, [name] or [name] will refer to the provided instructions and notify site Pl/coordinator of dose status (increase, decrease, or maintain) for individuals assigned to a dose adjustment.

Active Treatment Arm: Based on the everolimus PK level, [name], [name], or [name] will determine whether a dose adjustment is warranted, i.e. the value falls outside the range of 5-15 ng/ml. The unblinded physician(s) will notify the local research team and PI how to proceed with next dose (increase by 2.5mg, decrease by 2.5mg, or maintain dose). Following any dose adjustments, a blood sample will be redrawn two weeks (+/- one week) after the modification. The unblinded physician will assess the everolimus PK level and notify the local study team to maintain or adjust the dose accordingly to achieve the target range of 5-15ng/ml. This process will be repeated until the everolimus level falls within the target range.

Dose adjustments in the open label phase of the study will be made by the site principal investigator. The PK value taken at the Month 1 visit will be released to the site physician by the unblinded coordinator and dose adjustments will be made based on the value.

A detailed explanation of other permitted dose adjustments can be found in Section 7.7.3.

